[figure not shown]

## 2 Introduction

The National Awareness and Early Diagnosis Initiative (NAEDI), a collaboration of Cancer Research UK, DH and National Cancer Action Team, has funded the implementation and associated research project of a health promotion intervention to promote early presentation in older women with breast cancer. The intervention (the Promoting Early Presentation (PEP) Intervention) was originally developed by Kings College, London and was the subject of a successful randomised control trial of older women aged 67+ attending for mammography screening, where the intervention was delivered by radiographers. The ultimate aim of the PEP Intervention is to equip women with the knowledge, skills, confidence and motivation to present promptly to their GPs on discovering breast symptoms, and thereby improve survival. The study found that the PEP intervention increased breast cancer awareness more than four-fold after two years compared with usual care2,2a.

This protocol details a follow-on research project which aims to determine the efficacy of the intervention when it is delivered in a general practice setting. The main health outcome of interest is breast cancer awareness, measured during recruitment to the project, one month after receiving the intervention and twelve months after receiving the intervention. The project has the support of the Primary Care Research Network (East Midlands and South Yorkshire) and is eligible for adoption onto the NIHR portfolio.

### 3 The Promoting Early Presentation (PEP) Intervention: rationale

Older women have a higher incidence and worse survival rate from breast cancer than younger women. In the UK, five-year survival from breast cancer is lower than in comparable Western European countries. The excess mortality seen in England compared with Norway and Sweden is especially pronounced in the first year after diagnosis, suggesting that late diagnosis is responsible for worse survival. Excess mortality is most marked in the older age groups. The latest figures from Trent Cancer Registry (2008) for breast cancer incidence show that over 25% of cases in the East Midlands are diagnosed in women over 70 years of age and over 40% of breast cancer deaths are in women over the age of 70 (2009). This project is to be located in Northamptonshire, Leicestershire and Rutland where the experience is close to the East Midlands median.

Between 17% and 35% of women with breast cancer delay presenting for more than three months after discovering symptoms, and delay in presentation is associated with worse survival. Older women are at even higher risk of delay in presentation than younger women. Other risk factors for delay include less education, non-lump symptoms, and not recognising the symptoms as serious. Older women have particularly poor knowledge of non-lump symptoms and the increase in breast cancer risk with age. About 20% of older women report that they never look at or feel their breasts.

This evidence suggests that low levels of knowledge about risk of developing breast cancer and symptoms, and lower confidence, skills and motivation to detect symptoms and seek help appropriately may contribute to the worse breast cancer survival experienced by older women. Among older women there is a very high chance that a breast symptom is one of breast cancer: one study found about 26% of women aged 70-79 referred to secondary care for investigation of breast symptoms were subsequently diagnosed with breast cancer compared with 7.6% of women aged 50-59.

A systematic review has shown there to be very limited evidence of the efficacy of existing interventions in promoting early presentation in breast cancer.

#### **4 The Promoting Early Presentation (PEP) Intervention: description**

The PEP Intervention on which this research is based is a scripted one-to-one interaction between a healthcare practitioner and an older woman supported by a booklet. This was designed to be delivered during a routine appointment on the NHS Breast Screening Programme but is applicable to other settings. It takes around 6 minutes to deliver. The style of delivery of the intervention is collaborative and motivational, with key messages being delivered positively. The booklet is given to the woman to take home.

To deliver the intervention, the healthcare practitioner must undertake a training package consisting of two formal group training sessions of 2 hours each, separated by two to three weeks. This training has been developed for radiographers and will be adapted to suit the needs of practice nurses. Kings College London will develop and run a one day 'train the trainers' course which will be delivered to two members of the project team: an experienced healthcare educator from the University of Northampton and an experienced member of the communications staff at NHS Northamptonshire (the training team). The training team will then jointly run two group courses for practice nurses from the participating practices, with up to 12 nurses in each group.

The PEP Intervention aims to address deficits in knowledge, motivation, confidence and skills associated with delayed presentation of breast cancer (see Box 1). These elements of the intervention were identified from a systematic review of the evidence on the risk factors for delay in diagnosis in breast cancer, interview studies in women with breast cancer, and surveys of knowledge and beliefs about breast cancer in the general female population.

### **Box 1: Key elements of the PEP Intervention**

#### **Informing**

*Risk of developing breast cancer:* Lifetime risk of developing breast cancer and increase in risk with age.

*Breast cancer symptoms:* The range of breast cancer symptoms, with emphasis on non-lump symptoms, supported by photographs of signs of early breast cancer.

#### **Motivating**

*Persuasive goal-setting message* strongly recommending immediate help-seeking in the event of symptom discovery.

*Persuasive messages targeting attitudes and social norms* in the booklet. These outline the benefits of prompt help-seeking and suggestions for overcoming barriers to seeking medical help, such as embarrassment and fear about cancer treatments. They are supported by cartoon illustrations and affirming quotes.

#### **Providing self-efficacy and skills to perform target behaviours (breast checking and seeking medical help promptly on discovering a breast change)**

*Breast cancer awareness skills* are demonstrated by the health professional using a silicone breast model followed by guided practice with positive feedback to increase women's confidence to detect a breast change.\*

*Social skills* are modelled with cartoon illustrations and dialogue in the booklet showing (a) how to seek medical attention immediately and (b) how to disclose symptoms to someone close in the event of discovering a breast change.

*Self-regulatory skills* to prioritise the target behaviours in the face of other demands through action planning are prompted using an 'if-then' model (for example, "if I discover a breast symptom, then I will make an appointment to see a GP").

\*This is not a tutorial in Breast Self Examination, as there is currently insufficient evidence of its effectiveness (a Cochrane systematic review found that Breast Self Examination had no effect on breast cancer mortality but increased investigations). The PEP Intervention provides only simple guidance in techniques for breast checking.

To address psychological barriers to early presentation, the PEP Intervention targets key elements of behavioural control specified by the Information-Motivation-Behavioural skills

model. It also draws upon insights from self-regulation theory, the theory of planned behaviour and models of specific planning and implementation intention formation. The PEP Intervention seeks to highlight knowledge of symptoms and risks (without arousing fear) and to provide expertise in symptom recognition. It also seeks to bolster the motivation to seek help through setting goals, and to target key elements of motivation, including positive expectations of the outcomes of seeing a GP (e.g. feeling reassured) and approval from family and friends for having sought help. In addition, the PEP Intervention seeks to enhance confidence to take part in the social interactions involved in early presentation and prompts formation of intentions to detect a breast change or present promptly to a GP, which will facilitate behaviour change when necessary.

## **5 The Promoting Early Presentation (PEP) Intervention: efficacy**

Kings College London have carried out a randomised controlled trial to test the effect of the PEP Intervention on breast cancer awareness compared with usual care. This study randomised 867 women attending their final routine breast screening appointment at three breast screening services in the South East between July 2007 and May 2008 to the PEP Intervention, a booklet alone or usual care. At one year, the PEP Intervention increased breast cancer awareness to a much greater degree than other interventions of this kind.

The proportion of women who were breast cancer aware at one year was significantly greater in the two intervention arms than usual care (PEP Intervention: 24% versus 4%; odds ratio 15.2, 95% confidence interval 4.8 to 47.8; booklet alone: 12% versus 4%; odds ratio 3.5, 95% confidence interval 1.2 to 10.5). At two years, the proportion of women who were breast cancer aware was still significantly greater than usual care in the PEP Intervention arm, but not in the booklet alone arm2a (PEP Intervention: 21% versus 6%; odds ratio 8.1, 95% confidence interval 2.7 to 25.0; booklet alone: 9% versus 6%; odds ratio 1.8, 95% confidence interval 0.6 to 5.3).

The KCL team have also worked with NHS Breast Screening Programme to implement the PEP Intervention in three breast screening services, delivered by NHS mammographers rather than research radiographers. Preliminary findings over a period of several months showed that among 311 women who received the PEP Intervention, the proportion breast cancer aware increased from 3% to 39% over one month, compared with 3% to 4% in a service where it was not offered (report in preparation).

## 6 Research project

### 6.1.1 Research questions

This project aims to investigate the effectiveness of the Kings College interventional programme when implemented in a general practice setting, delivered by practice nurses. If increased breast awareness is seen in this setting, it will potentially lead to a sustainable model of improving the early presentation of breast cancer symptoms in women aged over 70 years. This is a group that are known to have lower breast cancer awareness, are more likely to delay presentation in breast cancer, and have worse outcomes than younger women.

The primary research question for the study is therefore:

***Does the Promoting Early Presentation (PEP) intervention increase breast cancer awareness in older women (over 70 years) when used in a general practice setting?***

Secondary research questions:

- *Which, if any, demographic factors are associated with successful PEP intervention in primary care settings?*
- *What are the barriers to successful outcomes from a service user perspective?*

### 6.1.2 Methods

The efficacy of this intervention in a population of older women attending for mammography screening has already been established in a randomised control trial. This study will investigate whether the intervention is also effective when implemented in a more general primary care setting, and will use observational methods to compare participants' breast awareness before and after the delivery of the PEP intervention (both in the short and long-term).

Participants (for sampling and recruitment methods see 6.1.3 and 6.1.4) will be asked to complete a **validated measure of breast cancer awareness** (the Breast Cancer Awareness Measure) on three occasions: during recruitment to the project, again one month after they have had the educational intervention and 12 months after the intervention. Additionally, participants will be asked to complete a **short questionnaire** relating to demographic and socio-economic information. This will enable the research team

to collate information about those factors previously identified as being associated with reduced use of health services:

- Age
- Postcode (for Indices of Multiple Deprivation analysis)
- Ethnicity
- Details of first/second language
- Formal education level
- Disability
- Transport provision
- GP surgery (for calculation of distance between residential location and surgery)

The intervention training will be delivered to each participating practice nurse by staff of the University of Northampton and NHS Northamptonshire who have been trained to do so by the Kings College team (for details, see section 4). The trained practice nurses will then deliver the intervention as part of this project.

The demographic questionnaire completed by participants will also ask for the contact details of those who are willing to be contacted for a short telephone interview at the conclusion of the research project. Following initial analysis of the 12 month follow up measure, participants who have shown little or no raised awareness from their scores (and who have consented to participate) will be invited to complete a **short telephone interview** with a researcher. A stratified sample will be drawn from those who consent to being contacted. Stratification will be undertaken according to the factors identified above which are associated with reduced use of health services. The interviews will explore the reasons why the intervention was unsuccessful with these individuals. It is anticipated that approximately 15 telephone interviews will be undertaken, but the final number will depend on when data saturation occurs.

### *6.1.3 Sample size*

The primary research question of the proposed study will test the null hypothesis that there is no relationship between the validated Breast Awareness scale outcome (not aware vs. aware) and the time at which the outcome was measured (before vs. 12 months after). This will be tested by the McNemar test for paired proportions. The criterion for significance (alpha) has been set at 0.05 (2-tailed).

The power analysis is based on the following population effect size, derived from previous research: in 90.0% of pairs, both cases will be classified as not aware and in another 4.0%

both cases will be classified as aware. These cases contribute no information to the hypothesis test.

A discrepancy between the two members of a pair is expected in the balance of the population: 1.0% of all pairs will show an outcome of aware for the before case only, while 5.0% of all pairs will show an outcome of aware for the after case only. This effect was selected as the smallest effect that would be important to detect, in the sense that any smaller effect would not be of clinical or substantive significance. This effect size is reasonable, in the light of results from previous research in this field.

A proposed sample size of 250 (at 12 month follow-up) will have power of 80.7% to yield a statistically significant result. The attrition rate between baseline and immediately after the intervention will be low as the participants will bring their completed questionnaire to their booked appointment and complete the post-intervention questionnaire immediately after their appointment (estimated 5% drop-out). However, the drop-out rate to the 12-month follow-up is likely to be substantial and has been conservatively estimated at 50%. Hence 532 participants will need to be recruited for the intervention in order to ensure that 250 are available for analysis after 12 months.

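### The stated 80.7% power is about 4 points too high for the uncorrected or mid-p McNemar test, and no usual version of the test reaches it

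*Protocol*

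**What the plan says.** All the inputs are in section 6.1.3 of the protocol. The null hypothesis is that awareness (aware or not aware) is unrelated to time (before or 12 months after). On the test: "This will be tested by the McNemar test for paired proportions". On the level: "The criterion for significance (alpha) has been set at 0.05 (2-tailed").

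The assumed population has 90.0% of pairs not aware at both times and 4.0% aware at both times. Of these the protocol says: "These cases contribute no information to the hypothesis test". The remaining 6.0% are discordant: "1.0% of all pairs will show an outcome of aware for the before case only", and "5.0% of all pairs will show an outcome of aware for the after case only". The protocol describes this as the smallest effect worth detecting.

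It then concludes: "A proposed sample size of 250 (at 12 month follow-up) will have power of 80.7% to yield a statistically significant result". It allows for 5% early drop-out and 50% drop-out by 12 months, and sets recruitment at 532. Neither section 6.1.3 nor section 6.1.5.1 says which version of the McNemar test is meant, and no power formula is named.

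**The concern.** The test uses only the discordant pairs, and 250 × 0.06 = 15 of these are expected. With so few informative pairs the test statistic is coarse, and large-sample power formulas can miss the true rejection probability by several points. A power printed to one decimal therefore needs checking against the test itself.

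The stake is how a non-significant result would be read. At the effect the protocol chose as its minimum, 80.7% power implies a 19.3% chance of a miss. If the true power is about 77%, that chance is about 23%, and the design falls just below the customary 80% that the printed figure appears to clear.

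**Working it through.** **Inputs (protocol, section 6.1.3).** Aware after only: p01 = 0.05. Aware before only: p10 = 0.01. Total discordance: 0.06. Given discordance, the probability that a pair goes in the after-only direction is 0.05/0.06 = 5/6. Pairs: n = 250. Two-sided alpha: 0.05.

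**Step 1: reproduce the printed figure.** Take exactly 15 discordant pairs and use the arcsine approximation for 5/6 against 1/2:

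- h = 2·asin(√(5/6)) − 2·asin(√(1/2)) = 2.3005 − 1.5708 = 0.7297
- power = Φ(0.7297 × √15 − 1.960) = Φ(2.826 − 1.960) = Φ(0.866) = 0.8068

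This is 80.7% to the printed decimal. Other formulas do not match it:

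- Conditional normal with 15 pairs: Φ((1/3 × √15 − 1.960 × 0.5)/√(5/36)) = 79.8%
- Unconditional normal: Φ((0.04 × √250 − 1.960 × √0.06)/√(0.06 − 0.0016)) = 73.6%
- Miettinen second-order: 77.8%

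These approximations spread over 7 points, so the enumerated power has to decide.

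**Step 2: exact power with 15 discordant pairs.** With 15 pairs, all four versions of the test reject when 12 or more, or 3 or fewer, go in the after-only direction. Under Bin(15, 5/6) the probabilities of 12, 13, 14 and 15 are 0.2363, 0.2726, 0.1947 and 0.0649. They sum to 0.7685, and the lower tail adds nothing visible. Power is 76.8%, already about 4 points below the arcsine value for the same 15 pairs.

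**Step 3: exact power with 250 pairs.** Let the discordant count K follow Bin(250, 0.06) and the after-only count given K follow Bin(K, 5/6). Sum the probability of each version's rejection region:

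| McNemar version | Power at n = 250 | Gap to 80.7% | Pairs for 80% power |
|---|---|---|---|
| Uncorrected | 77.0% | 3.7 points | 267 |
| Mid-p | 76.7% | 4.0 points | 269 |
| Exact | 69.3% | 11.4 points | 307 |
| Continuity-corrected | 67.8% | 12.9 points | 317 |

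**Step 4: where the gap comes from.** For the uncorrected and mid-p tests, letting K vary hardly moves the result (76.8% with K fixed; 77.0% and 76.7% with K random). Their shortfall comes from the approximation. Variation in K costs power only for the exact and continuity-corrected versions, which fall from 76.8% to 69.3% and 67.8%.

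**Step 5: does the recruitment figure leave slack?** 532 × 0.95 × 0.50 = 252.7 pairs. With about 253 pairs the uncorrected test still has less than 78% power.

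**Step 6: level.** Under a null of 3% v 3% with n = 250, the same enumeration gives a rejection rate of 4.7% (uncorrected), 4.6% (mid-p), 2.7% (exact) and 2.4% (continuity-corrected).

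**The case against.** The strongest reply is that this changes nothing in the design. The protocol names a plain McNemar test, most naturally read as the uncorrected one, where the gap is 3.7 points. That is smaller than the uncertainty in the inputs: with 0.8% instead of 1.0% aware before only, uncorrected power would be about 83%. The earlier randomised trial summarised in section 5 saw much larger effects (24% v 4% at one year), and at effects of that order 250 pairs are ample. The choice of McNemar version may also properly sit in a statistical analysis plan that is not shown.

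Much of this stands. The gap is modest under the plain reading, and leaving the version open is not in itself a fault in a protocol. But uncertain inputs do not excuse a wrong output. The protocol fixes its inputs, attaches a power to them and chooses to power at the minimum important effect. An analysis plan cannot correct a figure printed here.

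Three stronger readings are tempting, and the document supports none of them:

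- A reader might infer that true power is about 68%. That holds only for the exact or continuity-corrected test, and the protocol names neither.
- A reader might infer that the mistake was to treat 15 discordant pairs as fixed. Step 2 shows that this does not explain the gap for the uncorrected or mid-p test.
- A reader might take the arcsine origin as established. The match is to the printed decimal, but it is an inference, and the conclusion does not depend on it.

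**Conclusion.** The stated power is wrong for the stated test and inputs. At n = 250 with 5.0% v 1.0% discordance and two-sided 0.05, power is about 77% with the uncorrected or mid-p McNemar test, 69% with the exact test and 68% with continuity correction. The overstatement is about 4 points under the plain reading. It reaches 11 to 13 points only if a conservative version is used.

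This rests on the protocol's own discordance rates and on independent pairs; no outside figure is used. It is an error in a reported number. It does not show that the trial is badly underpowered or that 532 is the wrong recruitment target.

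**What to change.** In section 6.1.3, replace the stated power with: *power of about 77% (uncorrected or mid-p McNemar test; about 69% if the exact test is used)*. In the same place, name the version to be used, uncorrected or mid-p. Either is acceptable: both hold the 5% level at the planned 6% total discordance (4.7% and 4.6% at 3% v 3%), and both keep about 7 points of power over the exact test. A move to mid-p is optional.

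Leave the recruitment target unchanged. The cost is one sentence and a slightly less favourable stated power.

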#### *6.1.4 Recruitment*

The participating GP practices will be recruited through the Primary Care Research Network (EM SY) and the participating practice staff will have undergone training in the conduct of research.

The study participants will be women over the age of 70 years. This is a group that are known to have lower breast cancer awareness, are more likely to delay presentation in breast cancer, and have worse outcomes than younger women. This age group is the focus of work being undertaken by the East Midlands Cancer Network. Currently women over the age of 70 years do not receive a routine invitation for NHS breast screening (this facility will be extended to women aged 71-73 by 2016). An estimated 18 GP practices, identified via the PCRN, will recruit approximately 30 participants each to the study (to a total of 532 participants). The recruitment of the participants for the study will be done via the GP practices, who will identify those eligible for inclusion, send out invitation letters and the pre-intervention questionnaire. The GP practices will arrange the appointments and deliver the intervention. The post-intervention questionnaires will be sent out by the practices. All

completed questionnaires, linked with a unique identifier, will be returned by the participants to their GP practice, who will then forward them to the CHWR for analysis.

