- Data storage and transfer: No personal contact information will be stored with data collected as part of the completion of the project and research questionnaires will not be linked to patient medical records. Each participant will have a unique identifying number in order to link the data collected from them in the three Breast Cancer Awareness Measures and the demographic questionnaire. However, only the practices, who will be responsible for contacting the participants, will have the key to link these identifiers with names and addresses. This key will be stored securely, and separately from the medical records. The University research team will therefore not have access to the personal identifiable information of participants, except for those patients who opt to form part of the telephone interview sample. For this sample, the University team will keep the contact details of those who volunteer this information, together with their unique identifier, separate from their data which will be stored with only the unique identifier. Research questionnaires will be securely transferred to the University team and the hardcopies of these will be stored in a locked cabinet. All data collected as part of the project shall be stored securely according to the guidelines set by the Data Protection Act (1998) and the Freedom of Information Act (2000). All electronic information will be filtered with anti-virus software. All data collected as part of the research will be destroyed 5 years after the conclusion of the project.
- Feedback: The results of the study will be made available to the general public via the normal public communications employed by NHS Northamptonshire.
- Additional issues: It is possible that participants may become anxious as a result of their breast cancer awareness intervention, although this project has been carefully designed to minimise the likelihood of this and interventions will be delivered by qualified practice nurses. The practice nurses are ideally placed to reassure participants and, should it be necessary, can refer them to their GP for further discussions.

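### Completed awareness questionnaires go back to the practice that delivers PEP and holds the name key, an avoidable risk of reporting bias of unknown size in an uncontrolled before-after comparison

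*Protocol*

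**What the plan says.** The protocol gives the GP practice four roles.

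- **Delivery.** Section 6.1.4: "The GP practices will arrange the appointments and deliver the intervention". Section 6.1.2 names the staff: "The trained practice nurses will then deliver the intervention as part of this project".
- **Distribution.** Section 6.1.4: "The post-intervention questionnaires will be sent out by the practices".
- **Collection.** Section 6.1.4, of every form: "completed questionnaires, linked with a unique identifier, will be returned by the participants to their GP practice". The practice passes the forms on, and the CHWR analyses them.
- **Identification.** Section 6.1.6, under data storage and transfer: "only the practices, who will be responsible for contacting the participants, will have the key to link these identifiers with names and addresses".

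Section 6.1.3 adds that "participants will bring their completed questionnaire to their booked appointment and complete the post-intervention questionnaire immediately after their appointment". Section 2 and Sections 6.1.2 and 6.1.5 instead place the first follow-up at one month. Those statements need reconciling, but under either timing Section 6.1.4 sends the form through the practice.

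The primary comparison (Sections 6.1.2, 6.1.3 and 6.1.5) is a McNemar test of aware v not aware in the same women before and after the session, with no control group. The stated safeguards are the unique identifier, a University team without names (except for interview volunteers), a key stored apart from the medical records, no linkage to those records, secure transfer, and anonymity in publications.

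**The concern.** The identifier conceals a woman from the University but not from her own surgery, which holds the key and receives the form first. With about 30 women per practice, matching a form to a person would be easy for anyone who has the key. The outcome is built from the woman's own answers, given after a one-to-one session meant to inform and persuade. After that session she knows which answers are hoped for, and the form goes back to the organisation that taught her.

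Because the baseline form follows the same route, a fixed tendency to please the surgery affects both measurements and drops out of the paired comparison. What does not drop out is any change in that tendency brought about by having been taught. In a single-group design such a change looks the same as a gain in awareness, and no later analysis can separate the two. The same binary outcome feeds the demographic regression. The telephone interviews draw on women whose scores show little or no gain, so over-reporting would also remove from that pool some of the women the study wants to hear from.

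**Working it through.** **1. Is the form identifiable to the organisation that teaches?** Set side by side, Sections 6.1.2 and 6.1.4 (delivery by practice nurses), 6.1.4 (forms returned to the practice) and 6.1.6 (key held only by the practices) answer yes. None of the listed safeguards hides a woman's answers from her practice, and the protocol describes no sealed or direct return.

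**2. The plan's own power figure.** Inputs from Section 6.1.3: n = 250 pairs, 1.0% aware before only, 5.0% aware after only, two-sided alpha 0.05.

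- Expected discordant pairs: 250 × (0.01 + 0.05) = 15.
- Arcsine effect size: h = 2·asin√(5/6) − 2·asin√(1/2) = 0.730.
- Power = Φ(h√15 − 1.96) = 80.7%, which matches the stated 80.7%.
- Net gain the study is sized to detect: 250 × (0.05 − 0.01) = 10 women.

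**3. What a reporting shift would do.** Assume no true change, with discordance b = 1% before only and c = 1% after only. Let a net share q of all women be recorded as aware only after the session through altered reporting, so that c = 1% + q. The documents give no value for q, so it is varied.

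The number of discordant pairs is M ~ Bin(250, b + c). Given M, the after-only count is K ~ Bin(M, c/(b + c)). The uncorrected test rejects when (2K − M)² > 1.96²·M. The exact test rejects when the two-sided binomial p is at most 0.05. Summing over M and K gives:

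| q | Women (250 × q) | Discordance, after v before | Uncorrected McNemar | Exact McNemar |
|---|---|---|---|---|
| 0 | 0 | 1% v 1% | 4.6% | 0.9% |
| 1% | 2.5 | 2% v 1% | 13.2% | 6.9% |
| 2% | 5 | 3% v 1% | 33.3% | 24.1% |
| 3% | 7.5 | 4% v 1% | 57.3% | 47.5% |
| 4% | 10 | 5% v 1% | 77.0% | 69.3% |

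The last row is the design alternative itself: a 4-point shift in reporting would be indistinguishable from the effect the study is sized for. Its 77.0% and 69.3% are the fully enumerated counterparts of the 80.7% approximation.

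**4. What the table does not show.** It describes any upward shift, whatever its cause. It does not say how much of a shift the return route would produce, or how much a different route would remove.

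**The case against.** A good deal can be said on the other side.

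- **No evidence that it will happen.** Nothing in the protocol shows that courtesy answers will occur. A reader might infer that women report to the nurse who taught them and that she reads the answers. The text says only that forms go to the practice and are forwarded; it does not say who handles them or whether anyone opens them. The information sent with the questionnaire is not shown and may deal with this. This stands, and it limits the point to a risk.
- **Knowledge items resist courtesy.** The intervention covers non-lump symptoms and rising risk with age, and a woman cannot politely supply knowledge she lacks. Section 5 also suggests a demanding threshold: 4% of usual-care women and 24% of PEP women were aware at one year in the earlier trial. This stands. Self-reported checking or confidence would be more exposed, but the items are not given. For the same reason, one cannot infer that women would have to disclose worry or failure to check to their surgery.
- **Time and baseline.** The sample size rests on 12 months, long after a session of about six minutes, and the baseline form, described as "participants will bring their completed questionnaire to their booked appointment", goes to the same practice. Both weaken a differential shift. Neither rules one out.
- **The figures are not specific.** The 2% and 3% are assumed, and they show how vulnerable any uncontrolled comparison is. Against the earlier 24% v 4%, a shift of 2 or 3 points is small. That is fair, but this study is sized for a net gain of 4 points.
- **Safeguards exist.** Practice staff are trained in research conduct, the CHWR does the analysis, and the key is kept apart from the records. These lower the stakes without hiding the answers from the practice.

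**Conclusion.** The point holds as a risk of bias that the protocol creates by fixing the return route and could cheaply reduce. The facts about delivery, the key and collection are stated outright. That a change in reporting would be counted as effect follows from the lack of a control group.

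The size is unknown. Rejection rates of about 33% and 57% (exact 24% and 48%) rest on assumed net shifts of 2% and 3%, 1% background discordance in each direction, 250 pairs and no true change. They are illustrations only. A reader might take them as the false-positive rate that the return route causes, or conclude that a positive result could not be believed. The documents support neither reading. This is a worthwhile procedural improvement, not a wrong figure or an invalid test.

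**What to change.** In Section 6.1.4:

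- Supply a sealed reply-paid envelope addressed to the CHWR with each of the three questionnaires. A form handed in at the appointment should be sealed and forwarded unopened.
- State on the form that practice staff will not see the answers.
- Have the CHWR tell each practice only which identifiers have been returned. Completing a questionnaire serves as consent under Section 6.1.6, so practices need to know that a form came back, but not what it says.

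The 6.1.3 sentence about bringing the completed form to the appointment should be aligned with this. Names stay with the practices as Section 6.1.6 requires, and the sample, visits and test are unchanged.

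The cost is modest postage for at most 3 × 532 = 1,596 envelopes, plus a periodic returns list. The change would reduce social-desirability reporting but not abolish it, since women would still know that their surgery gave the session and sent the form.
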